1.5.2 Risks related to the study design and required procedures

Aerucin® will be administered in addition to standard-of-care antibiotic therapy, as determined by the investigator on the exclusive basis of the medical needs of his/her patient. Therefore, participation in this study does not affect the chances of a positive clinical outcome in any given study subject, also taking into account the favorable safety profile of the investigational product.

Except for blood sampling for PK and anti-drug antibody (ADA), and rapid testing of airway specimens for assessing the presence of *P. aeruginosa*, the procedures that are required for the study are all routine procedures, in nature and frequency, for this type of patients whose clinical status requires hospitalization in an ICU. Therefore, with the exceptions noted earlier, this study does not impose an unreasonable burden on the study subjects.

Blood sampling for PK and ADA has been reduced to the minimum necessary by allowing sparse sampling for the majority of the study subjects, on the one hand, and by limiting the required sample volume to the minimum technically necessary for the assays, thus limiting the related burden as much as possible.

Eligible study subjects will be randomized and treated either on the basis of culture results (known from recent cultures) or on the basis of rapid diagnostic testing of airway specimens using devices such as CE marked Cepheid's GeneXpert® with Investigational / Research Use Only (IUO / RUO) PA Cartridge, BioFire Diagnostics, LLC (a BioMerieux company)'s IUO FilmArray® LRTI Panel (please refer to section 14.3). This approach is necessary to allow the study intervention to be implemented as early as possible in the course of the disease, as early treatment is a known driver of clinical outcomes. It is expected that the results of rapid testing will not be confirmed by standard microbial culture in a small number of subjects for various reasons including the possibility of rapid test false positive, inadequate samples, or sample cultures affected by an ongoing antibiotic treatment. This situation is not expected to occur in more than 5% of the randomized subjects. Considering the safety profile of Aerucin® and of similar fully human anti-infective mAbs, this risk is deemed acceptable in the context of this study protocol.

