 - a. An airway specimen culture positive by any method for *P. aeruginosa* of a specimen obtained less than 72 hours prior to randomization. A fresh airway specimen must be obtained prior to treatment initiation for standard microbial culture by the local laboratory (including organism identification, quantitative/semi-quantitative culture and susceptibility testing); the corresponding culture results are NOT required prior to randomization.

OR
 - b. A rapid diagnostic test (see section 14.3 for acceptable methods). In such case, the same sample must ALSO be used for standard microbial culture by the local laboratory (including organism identification, quantitative/semi-quantitative culture and susceptibility testing). The corresponding culture results are NOT required prior to randomization.

OR
 - c. A positive airway specimen culture by any method of *P. aeruginosa* from a specimen obtained at screening (quantitative, semi-quantitative).
8. APACHE II score ≥ 10 and ≤ 35 within 24 hours once subject has consented.

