4.2 Exclusion Criteria

1. The subject is moribund. Clinical judgment by the investigator that the subject is unlikely to survive the current illness/ICU-admission/treatment period despite delivery of adequate antibiotics for treatment of *P. aeruginosa* pneumonia.
2. Effective antibacterial drug therapy for the index pneumonia administered continuously for 48 hours or more prior to initiation of study treatment. Effective antibiotics would include those typically used to treat *P. aeruginosa*.
3. Plasmapheresis (ongoing or planned) or any procedure that would remove/filter out the monoclonal antibody/study drug.
4. Immunocompromised and at risk of infection by opportunistic pathogens including, but not limited to the following:
 - a. HIV / AIDS who are not stable under medication and/or most recent CD4 < 200.
 - b. Expected neutropenia due to chemotherapy.
 - c. Absolute neutrophil count less than 500/ μ L (mm^3).
 - d. Heart or lung transplant recipient within the past 6 months.
5. Known hereditary complement deficiency.
6. Liver dysfunction with a Child Pugh C score (Child Pugh score of A or B are acceptable at discretion of the Principal Investigator [PI]).

7. Pulmonary disease that precludes evaluation of a therapeutic response (such as lung cancer resulting in bronchial obstruction or on the same side as the pneumonia, active tuberculosis, cystic fibrosis, granulomatous disease, fungal pulmonary infection, lung abscess, pleural empyema or post obstructive pneumonia).
8. Patient has received intravenous (IV) immunoglobulin therapy within 3 months prior to the Screening Visit.
9. Any woman of child-bearing potential (WOCBP) who does not have a negative pregnancy test result at Screening using SERUM or URINE testing based on Beta-subunit human chorionic gonadotropin (HCG) standard tests and methods from the local laboratory. Non-pregnant and non-lactating with confirmation via local laboratory testing is required. Women who are post-menopausal as evidenced by the absence of menstruation for at least 1 year are eligible; the date of last menstruation is to be recorded in the study files unless post-menopausal status is obvious due to age.

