## 5.3. Microbiological Endpoints

The microbiological endpoints have the following:

1. Microbiological outcome as measured by the proportion of subjects with the index *P. aeruginosa* pneumonia based on the data provided by the local microbiology laboratory and central microbiology laboratory.
2. Proportion of subjects achieving the eradication of *P. aeruginosa* at Day 21 and 28. Eradication is considered as obtained when a specimen of respiratory secretions is obtained between the visit day and Day 28 and is negative. When no specimen is obtained within this time frame, microbiological outcome will be assessed as “Eradicated” only if the study subject is not receiving any antibiotic active against the initial strain after the study drug administration visit day and displays no signs and symptoms of pneumonia.
3. Change in bacterial load related to the index *P. aeruginosa* on the basis of quantitative or semi-quantitative cultures by the local microbiological laboratory.

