#### **6.2.3. Microbiological Intent-to-Treat Population (micro-ITT)**

The micro-ITT Population is defined as all ITT subjects for whom microbiological documentation of pneumonia due to *P. aeruginosa* at screening/baseline has been obtained.

The micro-ITT population will be used for efficacy analyses. Subjects will be analyzed by randomized treatment group.

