### 6.4.3. Microbiological Endpoints

Microbiological endpoints include the following:

- Eradication of index *P. aeruginosa* at Day 21 and 28;
- Re-infection/new infection defined as a reoccurrence of pneumonia due to *P. aeruginosa* within the 28-day follow-up period; and
- Change in bacterial load related to the index *P. aeruginosa* on the basis of quantitative or semi-quantitative cultures by the local microbiological laboratory.

Microbiological endpoints of eradication and re-infection/new infection will be determined based on quantitative/semi quantitative cultures performed by the local laboratory and testing of isolates performed by a central microbiology laboratory.

For microbiological outcome of eradication of index *P. aeruginosa*, if no specimen of respiratory secretions is obtained at the specific time point, the nearest microbiological data available prior to that day (Day 7, 14, 21, or 28) will be used, i.e. using LOCF approach. When there is no specimen obtained prior to that day, microbiological outcome will be assessed as “Eradicated” only if the study subject is not receiving any antibiotic active against the initial strain after the study drug administration and prior to that day and displays no signs and symptoms of pneumonia.

The eradication rate of index *P. aeruginosa* and reinfection rate of pneumonia due to *P. aeruginosa* will be summarized by treatment group based on the micro-ITT Population and analyzed using a stratified CMH test based on the stratification factors at randomization. The P-value from the stratified CMH test will be presented.

Change in bacterial load ( $\log_{10}\text{cfu/mL}$ ) related to the index *P. aeruginosa* based on the local microbiological laboratory will be presented by treatment group for the micro-ITT Population.

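### Eradication is scored in micro-ITT subjects whose last pre-dose culture is already negative for P. aeruginosa, so some can count as eradicated with no organism shown at baseline

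*SAP*

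**What the plan says.** - **Entry.** Protocol 4.1, criterion 7a, accepts "An airway specimen culture positive by any method for *P. aeruginosa* of a specimen obtained less than 72 hours prior to randomization". A new airway specimen must be taken before dosing and cultured locally, but randomization does not wait for the result.
- **Prior antibiotics.** Protocol 4.2, criterion 2, excludes effective therapy only if "administered continuously for 48 hours or more prior to initiation of study treatment". Shorter active treatment before dosing is allowed.
- **Population.** SAP 6.2.3 defines micro-ITT as ITT subjects "for whom microbiological documentation of pneumonia due to *P. aeruginosa* at screening/baseline has been obtained". Protocol 9.1.3 has the same rule. The only removal described for an unconfirmed culture (SAP 3.1, Protocol 3.1) concerns subjects positive on a rapid test.
- **Baseline.** SAP 6.1.1 takes the last assessment before study drug as baseline for every efficacy endpoint.
- **Endpoint.** SAP 5.3: "Eradication is considered as obtained when a specimen of respiratory secretions is obtained between the visit day and Day 28 and is negative".
- **Analysis.** SAP 6.4.3 says the eradication rate "will be summarized by treatment group based on the micro-ITT Population and analyzed using a stratified CMH test". If no specimen exists at the time point, the nearest earlier microbiology result is carried forward. Change in bacterial load is presented by arm in micro-ITT, without a test.

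**The concern.** Eradication is meant to describe the fate of an organism present when treatment began. As the rules stand, a 7a subject can have a negative culture on the day of dosing and another negative one later, and be reported as an eradication. The plan's own baseline value for that subject shows no *P. aeruginosa*. The load summary has the same difficulty, because there is no baseline load from which to fall.

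At stake is the reading of a stated microbiological objective (SAP 2.6) that also belongs to hypothesis 3 (SAP 6.1.3) and receives a P-value. Both arms' rates could be raised by subjects in whom no change can be shown, and a real difference among the others could be diluted.

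**Working it through.** **1. The rules side by side**

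| Subject | Qualifying evidence | Pre-dose culture | In micro-ITT? | Later negative specimen scored as |
|---|---|---|---|---|
| Route 7b | Positive rapid test | Negative | No (SAP 3.1) | Not analysed in micro-ITT |
| Route 7a | Positive culture, specimen under 72 h old | Positive | Yes | Eradicated |
| Route 7a | Positive culture, specimen under 72 h old | Negative | Yes: the earlier culture is documentation at screening, and nothing removes the subject | Eradicated |

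The last row is the gap. It follows from the slash in "at screening/baseline has been obtained" and the absence of any exclusion; no sentence states it outright. The event is plausible: the qualifying specimen may be almost 72 hours old at randomization and older at dosing, and active antibiotics may have run for just under 48 hours. Protocol 1.5.2 recognises "sample cultures affected by an ongoing antibiotic treatment", although it says so about the rapid-test route.

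**2. Carry-forward**

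Follow-up specimens are required only when medically indicated, before extubation, and at Day 28 if the subject is still intubated (SAP Table 1, note 1). The carry-forward rule in SAP 6.4.3 is not limited to post-dose specimens. Read literally, the pre-dose negative could itself become the eradication result.

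**3. Size (illustration only)**

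The documents give no eradication rate, no share of pre-dose negatives and no power for this endpoint, so there is no plan figure to reproduce. The only input from the plan is 77 per arm (SAP 4: 69/0.90 = 76.7, rounded up), with two-sided 0.05.

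Assumptions:
- f = share of micro-ITT negative before dosing: 10%, 20%, 30%.
- Eradication in pre-dose positives: p0 = 60% placebo, p1 = 80% active.
- Eradication in pre-dose negatives: q0 and q1.

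Formulas:
- Observed rates: a = f·q0 + (1−f)·p0 and b = f·q1 + (1−f)·p1.
- Difference: b − a = (1−f)(p1−p0) + f(q1−q0).
- Power: Φ[(b − a − 1.96·se0)/se1], where se0 = √(2m(1−m)/n), m = (a+b)/2, and se1 = √([a(1−a)+b(1−b)]/n).
- Full micro-ITT uses n = 77. The restricted analysis uses n = 77(1−f) with rates 60% and 80%.

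Worked case, f = 20% and q0 = q1 = 95%: a = 0.19 + 0.48 = 0.67 and b = 0.19 + 0.64 = 0.83. Then se0 = 0.0698, se1 = 0.0686, (0.16 − 0.1368)/0.0686 = 0.339, and power is 63.3%.

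| f | q0 / q1 | Observed rates | Difference (points) | Power, full micro-ITT | Power, pre-dose positives only |
|---|---|---|---|---|---|
| 10% | 95 / 95 | 63.5% vs 81.5% | 18 | 71.0% | 73.4% |
| 20% | 95 / 95 | 67% vs 83% | 16 | 63.3% | 68.2% |
| 30% | 95 / 95 | 70.5% vs 84.5% | 14 | 54.9% | 62.3% |
| 10% | 80 / 90 | 62% vs 81% | 19 | 74.7% | 73.4% |
| 20% | 80 / 90 | 64% vs 82% | 18 | 71.5% | 68.2% |
| 30% | 80 / 90 | 66% vs 83% | 17 | 68.1% | 62.3% |

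If the drug has no effect in pre-dose negatives (first three rows), the difference shrinks by the factor 1−f and restriction gains 2 to 7 points of power. If it adds 10 points in them (last three rows), the difference shrinks less and restriction loses 1 to 6 points.

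**The case against.** - **A negative culture is not clearance.** A reader might infer that the organism had gone before dosing and that the outcome in these subjects cannot depend on the drug. The documents do not support that. Protocol 1.5.2 lists antibiotic effect and inadequate samples as reasons why a culture fails to confirm a rapid test. A suppressed organism could regrow once antibiotics stop, and the antibody's half-life is given as about 3 weeks (Protocol 1.2). This stands, and it is why a power gain cannot be promised.
- **The frequency is unknown.** Only 7a subjects can be affected, and their share is not stated. The 5% ceiling in Protocol 1.5.2 concerns unconfirmed rapid tests. The 95% success rate is likewise an assumption: early deaths and subjects without later specimens may not be scored as successes. This stands.
- **The endpoint carries little formal weight.** It is outside the testing sequence in SAP 6.4.2, the trial is not powered on it, and bacterial load is only presented. This stands.
- **Keeping everyone with a documented index organism is a defensible micro-ITT principle.** It is, which is why the full result should stay in the report. It does not make a later negative interpretable as eradication when the baseline is negative.
- **The carry-forward rule probably means post-dose specimens.** Its fallback for subjects with no earlier specimen would rarely apply if pre-dose specimens counted. That is a fair reading of intent, but the text does not say it.
- **The adjudication committee assesses microbiological outcome (Protocol 9.5).** No rule is given to it for this case.

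**Conclusion.** The gap is real as a matter of definition. A 7a subject with a negative last pre-dose culture remains in micro-ITT, can be scored as eradicated, and enters the load summary with no organism shown at baseline. The effect is to raise eradication rates in both arms and, if the drug does little in these subjects, to dilute the difference: 20 points becomes 18, 16 or 14 at assumed shares of 10%, 20% or 30%. The actual size cannot be found from the documents.

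A reader might go further and infer that the rule favours the drug. It does not: pre-dose status is fixed before treatment, so randomization balances it in expectation. The primary endpoint and the ordered secondary tests are unaffected. The case for change rests on interpretability at low cost, not on a demonstrated loss of power.

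**What to change.** In SAP 6.4.3:
1. Analyse eradication and change in bacterial load in micro-ITT subjects whose last pre-dose airway culture grew *P. aeruginosa*.
2. Report the full micro-ITT eradication result alongside.
3. Tabulate pre-dose culture-negative subjects by arm.
4. Limit carry-forward for eradication to specimens taken after dosing.

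Clinical endpoints stay on the full micro-ITT population. The fresh culture is already collected, and selecting on a pre-dose status preserves the randomized comparison. The cost is a few lines of SAP text and one table, settled before unblinding. The drawback is fewer subjects in the restricted analysis, with less power if the drug also works in pre-dose negatives.

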## 5.4. Pharmacokinetic Endpoints

The pharmacokinetic endpoints are the following:

- Assessment of the PK parameters during full PK sub-study.
- Assessment of the PK parameters during sparse PK sub-study.

## **5.5. Safety Endpoints**

The safety endpoints are the following:

1. Assessment of clinical adverse events
2. Assessment of clinical laboratory safety tests
3. Assessment of immunogenicity to Aerucin®

## **6. STATISTICAL METHODOLOGY**

### **6.1. General Considerations**

#### **6.1.1. Definition of Baseline**

For all efficacy and safety endpoints, baseline is defined as the last measurement or assessment prior to the administration of the study drug.

#### **6.1.2. General Analysis Approach**

Categorical data will generally be summarized with counts and percentages of subjects. The denominator used for the percentage calculation will be clearly defined. Continuous data will generally be summarized with descriptive statistics including n (number of non-missing values), mean, median, standard deviation, minimum, and maximum.

The comparisons for the endpoints will be between the 20 mg/kg dose group and the placebo and will be performed at a two-sided 0.05 level of significance.

#### **6.1.3. Hypotheses**

1. Treatment of *P. aeruginosa* pneumonia with Aerucin® improves the rate of Clinical Cure of the index pneumonia.
2. Treatment of *P. aeruginosa* pneumonia with Aerucin® results in an increase in survival rate in the target population
3. Treatment of *P. aeruginosa* pneumonia with Aerucin® improves microbiological, functional and health economic outcomes overall.
4. Aerucin® at the proposed dose level is safe based on clinical observation, standard laboratory tests, and frequency and nature of related adverse events.
5. Aerucin® does not trigger an adverse immunogenic response (i.e., anti-Aerucin® immunogenicity).

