9.3 Statistical Methods

Continuous data will be summarized by means, standard deviations, median, min, and max. Categorical data will be summarized by frequency and percentages.

The primary endpoint of Clinical Cure rate at Day 21 will be analyzed using a stratified Cochran-Mantel-Haenszel (CMH) test. The CMH test will be stratified by baseline randomization strata. Time to Clinical Cure will be analyzed using a stratified log rank test. Other continuous endpoints will be analyzed using an Analysis of Covariance (ANCOVA), with treatment as a main effect, site, and baseline strata as covariates. Treatment by site interaction will be evaluated separately. Secondary endpoints will be analyzed using a sequential procedure in predefined order. Categorical variables will be analyzed using a stratified CMH test.

The primary comparisons for all endpoints will be between the 20 mg/kg dose group and placebo and will be done at 0.05 level of significance. The details of the planned analyses will be provided in the Statistical Analysis Plan.

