
#### 4. SAMPLE SIZE DETERMINATION

The primary efficacy endpoint is the proportion of subjects with Clinical Cure at Day 21.

It is assumed that the proportion of subjects with Clinical Cure will be 65% in the placebo group, and 85% in the 20 mg/kg dose group. With 69 subjects per group, there will be >90% power for a statistically significant difference at a two-sided 0.05 level of significance. Sample size calculation was performed based on Fisher's Exact test using binomial enumerations (PASS version 14). Assuming a 10% drop-out rate, approximately 154 subjects (77 per group) will be randomized.

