### **6.6. Safety Analyses**

Safety data will be summarized by actual treatment received and in total based on the Safety Population.

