### **6.6.1. Adverse Events**

An AE is defined as any untoward medical occurrence in a clinical investigation subject administered a pharmaceutical product, which does not necessarily have a causal relationship with this treatment. Adverse events, which include clinical laboratory test variables, will be monitored and documented from the time of randomization until 28 days after last dose. Adverse events will be coded using MedDRA (Version 19.1). Treatment-emergent adverse events (TEAEs) are defined as AEs that start on or after the administration of the study drug.

An overview of AEs will be provided including counts and percentages of subjects with the following:

- Any AEs
- Any TEAEs (overall and by maximum severity)
- Any drug-related TEAEs (overall and by maximum severity)
- Any serious AEs (SAEs) (overall and by maximum severity)
- Any drug-related serious AEs (overall and by maximum severity)
- Any treatment-emergent serious AEs (TESAEs)
- Any TEAEs leading to discontinuation of study drug
- Any AEs leading to death

The number and percentage of subjects with at least one TEAE will be presented by system organ class and preferred term. Drug-related TEAE, SAEs, Drug-related SAEs, and TESAEs will be summarized in the same manner. In the case of multiple occurrences of the same AE within the same subject, each subject will be counted only once for each SOC and preferred term.

Summaries will be provided by maximum severity for the number and percentage of subjects with TEAEs by system organ class and preferred term. For this summary, subjects with multiple adverse events will be counted only once by the maximum severity with in an SOC and preferred term.

Subject listings of SAEs, TEAEs leading to discontinuation of study drug, and AEs leading to death will be provided. All adverse events will be listed.

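### The safety hypothesis asserts that the drug is safe but sets no criterion, and no between-arm interval is planned for adverse events, so the report would not say how large an excess of harm has been excluded

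*SAP*

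**What the plan says.** Safety and tolerability is a primary objective (Protocol 2.2, SAP 2.2). Hypothesis 4 in SAP 6.1.3, repeated in Protocol 1.4, is that Aerucin "at the proposed dose level is safe based on clinical observation, standard laboratory tests, and frequency and nature of related adverse events". Neither document says how that hypothesis is to be judged.

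The first item under SAP 5.5 Safety Endpoints is "Assessment of clinical adverse events"; laboratory tests and immunogenicity follow. Two general sentences govern comparisons of endpoints:

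- Protocol 9.3: "The primary comparisons for all endpoints will be between the 20 mg/kg dose group and placebo", at the 0.05 level.
- SAP 6.1.2: comparisons for the endpoints "will be performed at a two-sided 0.05 level of significance".

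Neither sentence exempts safety. The word 'all' is in the Protocol only, and the two-sided specification is in the SAP only.

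The sections that actually plan the safety analysis are descriptive. SAP 6.6: "Safety data will be summarized by actual treatment received and in total based on the Safety Population". SAP 6.6.1: "An overview of AEs will be provided including counts and percentages of subjects with the following", and then "The number and percentage of subjects with at least one TEAE will be presented by system organ class and preferred term". Protocol 9.3.2 is also descriptive. None of them names a test, a between-arm difference, a confidence interval or a harm margin.

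By contrast, SAP 6.4.2.3 and 6.4.2.4 plan treatment differences with 95% confidence intervals for ventilation days, SOFA change, ICU stay and hospital stay.

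**The concern.** A hypothesis that a drug is safe can be supported only by showing that an excess of harm larger than some stated amount is unlikely. The plan has no such amount and no interval from which to read one. A report writer would have two routes to a conclusion on hypothesis 4: compare two percentages by eye, or use the general 0.05 wording. Neither says how much harm remains compatible with the data.

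The earlier human data are thin. The phase 1 study described in Protocol 1.5.1 had 16 healthy volunteers, 5 of them at 20 mg/kg. This trial is therefore the main source of comparative safety evidence in ventilated patients.

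Hypothesis 4 also names related events as one of its bases. Under Protocol 8.3.3, the definition of related requires that no other cause can be identified. In ventilated ICU patients another possible cause will often be present, so counts of related events may understate a real excess. The randomized comparison of all events does not depend on that judgment.

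**Working it through.** **Inputs.** SAP 4: "approximately 154 subjects (77 per group) will be randomized". The dropout step behind it reproduces: 69 / 0.90 = 76.7, rounded up to 77. The plan gives no power or precision figure for safety, so there is none to reproduce. Control rates of adverse events are not given either; the range below is an assumption. I take 77 treated per arm and two-sided 0.05.

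**Step 1: chance that a true doubling is not significant.** For control rate p and treated rate 2p, sum Bin(x; 77, p) × Bin(y; 77, 2p) over all pairs (x, y) that do not reject.

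| True rates | Missed, uncorrected chi-square | Missed, Fisher |
|---|---|---|
| 5% to 10% | 78% | 87% |
| 10% to 20% | 58% | 67% |
| 15% to 30% | 38% | 46% |
| 20% to 40% | 22% | 27% |
| 25% to 50% | 9% | 12% |

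The miss probability falls to 50% at a control rate of about 12% (chi-square) or 14% (Fisher). Below that a doubling is missed more often than not; above it, it is detected more often than not.

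**Step 2: sensitivity to the number treated.** If the 154 counts only microbiologically evaluable subjects, and up to 5% of those randomized are treated but not confirmed (Protocol 1.5.2), the Safety Population is about 154 / 0.95 = 162, or 81 per arm. The Fisher miss rates become 85% (5% to 10%), 65% (10% to 20%) and 25% (20% to 40%). The picture does not change.

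**Step 3: what an interval would show when the arms look the same.** Take 8 of 77 in each arm, so the observed rate is 8/77 = 10.4% and the difference is 0. The Wilson 95% limits for 8/77 are 5.4% and 19.2%. The Newcombe upper limit for the difference is

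√[(19.2 − 10.4)² + (10.4 − 5.4)²] = √(77.4 + 25.0) ≈ 10.1 percentage points.

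For other equal counts:

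| Events per arm | Upper 95% limit of the excess |
|---|---|
| 4 and 4 | +8.1 points |
| 8 and 8 | +10.1 points |
| 15 and 15 | +12.5 points |
| 23 and 23 | +14.2 points |

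**Step 4: what a p-value hides.** With 8 placebo and 16 Aerucin events out of 77 each, the observed difference is 8/77 = 10.4 points. Fisher gives p = 0.12, and the Newcombe 95% interval runs from about −1 to +22 points. The two percentages alone, or the p-value alone, would not convey that upper limit.

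**The case against.** **The safety sections plan no test.** SAP 6.6 and Protocol 9.3.2 are descriptive, and a specific section is normally read ahead of a general sentence. A reader might infer that the plan treats a non-significant safety comparison as support for hypothesis 4. The documents do not say so. That part of the objection stands. What remains is that hypothesis 4 has no criterion of any kind, and that the general wording is left open to that use.

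**A doubling is not always missed.** A reader might also infer that this trial would usually miss a doubling of any serious event. Step 1 shows otherwise from a control rate of about 15% upward. The only serious-outcome rates in the documents are high: Protocol 1.1 cites 20% to 33% pneumonia-attributed mortality as background. This stands too, and the statement about doubling is limited accordingly.

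**Much is already in place.** SAP 6.6.1 tabulates any TEAE by severity, SAEs, TESAEs and AEs leading to death, regardless of relatedness and by treatment received. Related events are only one of three bases named in hypothesis 4. Mortality is compared by stratified CMH (SAP 6.4.2.2), and an independent DMC with unblinded access reviews safety (Protocol 9.4). These are real safeguards. But the mortality analysis presents a p-value and survival plots with no interval for the difference, and DMC monitoring does not supply a final estimate. Any numerical limits in the DMC charter cannot be seen here.

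**Readers can compute the interval themselves, and an interval adds no power.** Both are true. A primary objective should still have its estimate prespecified, and the interval's purpose is to state the remaining uncertainty.

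**Conclusion.** The point holds in a limited form. Hypothesis 4 asserts safety without a criterion, and the planned output would not state what excess of harm has been excluded. The general 0.05 wording reaches the safety endpoints on its face without being meant, as far as the documents show, as a safety test.

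The low chance of detecting a doubling applies only below control rates of about 12% to 14%. That result rests on 77 treated per arm, independent binomial counts, unstratified tests and assumed control rates. The absence of a criterion and of an interval rests on none of these assumptions.

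This is a worthwhile, low-cost improvement. It does not bear on the efficacy analysis.

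**What to change.** 1. In SAP 6.6.1, add the Aerucin-minus-placebo risk difference with a 95% confidence interval (Safety Population, regardless of relatedness) for categories already tabulated: any TEAE, any TESAE, severe TEAE, and AE leading to death. Add the infusion-related and cardiovascular events monitored for 24 hours under Protocol 6.4, with the terms that define them listed before unblinding. Name the interval method, for example Newcombe.
2. Reword hypothesis 4 in SAP 6.1.3 as an estimation aim: to estimate the excess risk over placebo and report the upper limit of its 95% interval.
3. State in SAP 6.1.2 that safety endpoints are outside the 0.05 testing rule. Because Protocol 1.4 and 9.3 carry the same hypothesis and the wider wording, record there or in the SAP that this is a clarification.

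The cost is one extra table and some SAP wording, with no new data or patients. The limits will be wide (about 8 to 14 points even when the arms show equal counts, as in Step 3), so the safety statement will read less favourably than bare percentages would.
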